15.4.2 Secondary Analyses

CMV Status at Recurrence: Among patients who provide pathology at the time of tumor recurrence, a chi-square test will be used to compare treatment arms with respect to the

percentage of patients observed to be positive for antigen escape outgrowth at tumor recurrence. A paired t-test will be used to compare within each treatment arm the mean intensity of CMV antigen expression for primary and recurrent tumors. Alternative nonparametric methods may be considered if assumptions for parametric analytic methods are not satisfied. Though the original vaccination included Component A and B, the primary analysis of CMV status at recurrence will focus on only those patients who received Component A alone. However, additional exploratory analyses may include data from the few patients who received both vaccine Components A and B for whom we have info about CMV status at recurrence.

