8 HYPOTHESES AND OBJECTIVES

8.1 *Hypotheses*

- Our primary hypothesis is that:
 - Treatment of adult patients with newly diagnosed GBM using PEP-CMV during recovery from TMZ-induced lymphopenia in patients that are seropositive for CMV will be safe.
 - Treatment of adult patients with newly diagnosed GBM using PEP-CMV during recovery from TMZ-induced lymphopenia in patients that are seropositive for CMV will induce cellular immune responses through IFNy secretion of total Component A specific T cells using ELISPOT.
- Secondary hypotheses include:
 - Tumors are CMV antigen negative by immunohistochemical analysis and microarray analysis at the time of disease progression/recurrence.
- Exploratory hypotheses include:
 - The immune response to the PEP-CMV vaccine is detectable by pp65 ELISPOT.
 - The quality of immune responses determined by polyfunctional flow cytometry is multifunctional or monofunctional using the pp65 peptide in PEP-CMV.
 - Tregs will decrease after vaccination with PEP-CMV in combination with TMZ.
 - Different HLA haplotypes respond better to PEP-CMV vaccine in combination with TMZ.
 - At the time of disease recurrence, immunologic tumor cell infiltrate will be evident.
 - That PFS and OS within the 2 arms will provide information on the effects between the 2 TMZ regimens.

Treatment of adult patients with newly diagnosed GBM using PEP-CMV during recovery from TMZ-induced lymphopenia in patients that are seropositive for CMV will induce objective radiographic responses in this patient population in the subset of patients with residual disease.

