8.2.2 Secondary Objectives

- To determine if tumors are CMV antigen negative by immunohistochemical analysis and microarray analysis at the time of disease progression/recurrence.

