Effect of HLA haplotypes: Initially the distribution of HLA haplotypes (A, B, C, DR) will be described. Depending up the distribution of these haplotypes, the effect of HLA haplotype on outcome may be explored using the proportional hazards model (for OS and PFS) or linear regression (for some immune response outcomes). Analyses will adjust for treatment group. If possible, analyses will appropriately adjust for confounding variables.

Immunologic Cell Infiltrate: Within each treatment arm, changes in levels of infiltrating lymphocytes detected in primary and recurrent tumor specimens will be assessed using a paired t-test or its nonparametric analogue among patients who provide pathology at the time of tumor recurrence. When appropriate, a two-sample t-test will compare arms with respect to the change.

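### The secondary objective asks about CMV antigen loss in all recurrent tumours, but 15.4.2 plans only per-arm and between-arm tests, so no planned analysis answers it overall

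*Combined protocol and SAP*

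**What the plan says.** Section 8.1 gives one secondary hypothesis: "Tumors are CMV antigen negative by immunohistochemical analysis and microarray analysis at the time of disease progression/recurrence". Section 8.2.2 gives the matching objective: "To determine if tumors are CMV antigen negative by immunohistochemical analysis and microarray analysis at the time of disease progression/recurrence". Neither mentions an arm. Where the arm matters, the protocol says so: the second primary objective (8.2.1) asks which TMZ regimen gives the highest ELISPOT response, and the survival objective (8.2.3) is framed by arm.

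Section 15.4.2 sets out the analysis:

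- The set is limited to patients with tissue: "Among patients who provide pathology at the time of tumor recurrence".
- It is limited again by vaccine: "the primary analysis of CMV status at recurrence will focus on only those patients who received Component A alone". The word primary here selects a population and does not name a deciding test.
- Escape is compared between arms: "a chi-square test will be used to compare treatment arms with respect to the" percentage showing antigen escape.
- Expression is compared inside each arm: "A paired t-test will be used to compare within each treatment arm the mean intensity of CMV antigen expression for primary and recurrent tumors".
- The choice of test is left partly open: "Alternative nonparametric methods may be considered if assumptions for parametric analytic methods are not satisfied".

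The section has no analysis combined over arms, no significance level and no statement of which result answers the objective. The only split of alpha in the document (0.025, Section 15.2) belongs to the two primary endpoints.

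**The concern.** Both arms receive the same vaccine, and the objective is about what happens to the tumour antigen after it. Neither planned test answers that for the vaccinated group. The chi-square asks whether the arms differ in escape. The paired tests ask whether mean intensity changed in one arm at a time.

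Two things are at stake. First, the report could contain no overall figure for the one secondary question. Second, two small separate tests can easily disagree by chance. In a trial designed to compare TMZ regimens, one significant arm beside one non-significant arm invites a claim about regimen that the data do not support.

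**Working it through.** **Plan's own figure.** There is none for this analysis. The 81% power in Section 15.2 is for the ELISPOT comparison and is not at issue here.

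**Inputs from the documents.** Two arms, randomised 1:1 (11.4.2); a target of 26 evaluable Component A-only patients, 13 per arm (15.1); an unstated number with tissue at recurrence.

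**Assumptions.** Two-sided 0.05 per test; equal split of pairs between arms; a true standardised mean change d = 1.0 SD unless stated; totals of 10, 20 and 26 pairs as a range.

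**1. False positives.** The two per-arm tests use different patients, so they are independent. The chance of at least one false positive is 1 − 0.95² = 0.0975, or 9.75%. A single combined test at 0.05 has 5%.

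**2. Power of the paired t-test.** Power = P(|T| > t crit), where T is noncentral t with n − 1 degrees of freedom and noncentrality d√n.

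| Pairs in total | d | One arm | Pooled |
|---|---|---|---|
| 10 | 1.0 | n = 5, noncentrality 2.24: 40% | n = 10, noncentrality 3.16: 80% |
| 20 | 1.0 | n = 10, noncentrality 3.16: 80% | n = 20, noncentrality 4.47: 99% |
| 26 | 0.8 | n = 13, noncentrality 2.88: 75% | n = 26, noncentrality 4.08: 97% |

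**3. Disagreement between arms.** With 5 pairs per arm and the same true change of 1.0 SD in both, each test has power 0.401.

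- Exactly one significant: 2 × 0.401 × 0.599 = 0.48
- Both significant: 0.401² = 0.16
- At least one significant: 1 − 0.599² = 0.64

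**4. If antigen loss occurs in one arm only.** Take changes of 0 and 1.0 SD with 5 pairs per arm. The mean change over arms is 0.5 SD.

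- A simple pooled paired t-test has about 22% power (simulation), because the arm difference inflates the variance.
- A test stratified by arm uses the within-arm SD and 10 − 2 = 8 degrees of freedom. Its noncentrality is 0.5√10 = 1.58, which gives about 29%.
- The active arm tested alone has 40%.

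Under an equal change of 1.0 SD in both arms, the stratified test (noncentrality 3.16, 8 degrees of freedom) keeps about 79%, so stratifying costs almost nothing.

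**5. Precision of an overall proportion.** The exact (Clopper-Pearson) 95% CI for 5 negative of 10 recurrent tumours is 19% to 81%. For 10 of 20 it is 27% to 73%. The estimate would be imprecise, but it addresses the objective directly.

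**The case against.** **Per-arm reporting is a legitimate choice.** This is a randomised two-arm trial whose background (Sections 9.5 and 15.2) expects stronger responses under the 21-day regimen. If antigen loss is confined to that arm, combining the arms dilutes it, as step 4 shows. This stands. It is why the per-arm estimates should remain and the combined test should be stratified.

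**A pooled test of mean intensity would not answer the objective either.** Mean intensity can fall while every tumour stays positive. This also stands, and it is why the main analysis should be a proportion.

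Some stronger readings are tempting but not supported:

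- *Three tests of one hypothesis, or six with microarray, with a correspondingly larger error rate.* The between-arm chi-square has a different null. The two per-arm tests share no patients, so they cannot be correlated through common data. Section 15.4.2 does not plan to repeat each test on microarray, and Section 12.8 names IHC for antigen escape.
- *Splitting by arm halves the power.* That holds for one named arm at about 8 to 10 pairs. At 20 pairs it is 80% against 99%. Counting a result in either arm at 10 pairs gives 64% against 80%, though at the 9.75% error rate.
- *Pairs will certainly be few.* Section 11.1 and the Table 3 footnote on progression make tissue optional or conditional, but Section 12.8 asks for histologic documentation of progression unless contraindicated. The number is unknown.
- *The infiltrate analysis in 15.4.3 needs the same change.* It is also per arm ("Within each treatment arm, changes in levels of infiltrating lymphocytes detected in primary and recurrent tumor specimens will be assessed"), but it is already exploratory and needs no correction.

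**Conclusion.** The mismatch between objective and analysis is plain from Sections 8.1, 8.2.2 and 15.4.2 and depends on no assumption: nothing planned estimates antigen loss over all Component A-only patients. The size of the statistical cost does depend on assumptions. The 9.75% error rate assumes 0.05 per test and matters only if a significant result in either arm would be read as support, which the plan leaves open. The power loss assumes a similar change in both arms and an equal split of pairs; it is large at 10 pairs and modest at 20. The 48% chance of discordant arms applies to 5 pairs per arm at 1.0 SD. This is a secondary analysis, and the primary conclusions are unaffected. The correction is worth making because it is nearly free and supplies the missing answer.

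**What to change.** In 15.4.2:

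1. Name as the main analysis of the secondary objective the proportion of recurrent tumours that are antigen negative by IHC, over both arms, among Component A-only patients with tissue at recurrence, with an exact 95% CI. Specify pp65, the vaccine target that remains after Component B (gB) was removed.
2. Support it with one paired test of the primary-to-recurrent change in expression, combined over arms and stratified by arm.
3. Keep the per-arm changes and the between-arm comparison of escape as supportive results.

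The cost is wording only, with the same specimens and the IHC already planned. There is a small downside: the combined estimate averages over two TMZ regimens and is diluted if loss occurs mainly in one arm, so the per-arm estimates should stay in the report.

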15.4.3 Exploratory Immunologic Analyses

The following immunologic analyses will focus on patients who are evaluable for the immunologic monitoring primary analysis, i.e., patients who had immunologic monitoring conducted at baseline and prior to the second cycle of TMZ. These analyses will focus primarily upon patients who received only Component A. However, additional analyses may be conducted besides those described below.

Quality of Immune Response: The quality of the immune response will be assessed by polyfunctional flow cytometry. The analysis used here for polyfunctionality will be one that has been successful at distinguishing HIV progressors and non-progressors based on T-cell phenotype [115, 116]. All data will be background subtracted. For each measure, a lower threshold corresponding to two standard deviations above background is set to 0 based on a Poisson model essentially allowing T-cells to be designated as positive or negative for a certain phenotypic marker. The number of positive phenotypic markers post-vaccination will be calculated for each patient. The Kruskal-Wallis test will be used to compare treatment arms with respect to the number of phenotypic markers observed post-vaccination 3, as well as at vaccination 6. Additional exploratory analyses will be conducted using a Fisher's exact test that will compare treatment groups with respect to the proportion of patients with 5 positive markers, and 4 or more positive markers. Analyses similar to those described for the primary immunologic analyses will be used to examine the percentage of tetramer positive cells.

Analysis of covariance will be used to compare treatment groups with respect to the change between baseline and post-vaccination time-points in mean proliferative response and cytokine production, with baseline levels included in the model as a covariate. If assumptions of normality are not satisfied, the Kruskal-Wallis test will be used to compare treatment arms. Analyses will focus on the change between baseline and post-vaccination 3 assessments, as well as the change between baseline and vaccine 6.

Effect on Tregs: The mean levels of Tregs at baseline and at each follow-up assessment will be estimated within each treatment group. A mixed model that accounts for the correlation of repeated measurements within a patient will be used to compare treatment groups with respect to changes in Treg levels over time.

Effect of HLA haplotypes: Initially the distribution of HLA haplotypes (A, B, C, DR) will be described. Depending up the distribution of these haplotypes, the effect of HLA haplotype on outcome may be explored using the proportional hazards model (for OS and PFS) or linear regression (for some immune response outcomes). Analyses will adjust for treatment group. If possible, analyses will appropriately adjust for confounding variables.

Immunologic Cell Infiltrate: Within each treatment arm, changes in levels of infiltrating lymphocytes detected in primary and recurrent tumor specimens will be assessed using a paired t-test or its nonparametric analogue among patients who provide pathology at the time of tumor recurrence. When appropriate, a two-sample t-test will compare arms with respect to the change.

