9.4 Polyfunctional T-cell Responses and Anti-Viral Immunity

Protective immunity against acute and chronic viral infections requires effective T cell responses. While CD4 and CD8 T cell responses against viral infections that are rapidly cleared are characterized by polyfunctional effector functions including cytotoxicity (expression of CD107a), and the secretion of IFN γ , IL-2, and TNF α chronic infections often are typified by reactive T cells that are mono- or dual-functional, largely restricted to the secretion of IFN γ and TNF α , and unable to express and secrete IL-2[58-61]. Recent studies in HIV+ patients have demonstrated that the salient feature of T cell responses in patients who are long term non-progressors (LTNPRs) versus those who progress to AIDS, is the maintenance of polyfunctional HIV-specific T cell responses in LTNPRs[62-67]. Recent studies have demonstrated that polyfunctional T cell responses correlate with protection against CMV infection as well. Our preliminary data demonstrate that patients with GBM exhibit deficits in baseline CMV-specific polyfunctional immune responses *in vivo* but these deficits can be reversed *in vitro* by immunogenic stimulation with CMV antigens presented by autologous DCs. These findings may explain why CMV-infected tumor cells may persist in hosts with GBM and also suggests that proper vaccination *in vivo* could restore polyfunctional immune responses and mediate clearance of CMV-associated malignant gliomas (Figure 5).

[figure not shown]

Figure 5: Polychromatic Flow Cytometry to Analyze Polyfunctional CD4+ and CD8+ T cells: T cells isolated from a normal donor were stimulated for 6h *in vitro* with CMV pp65 peptide mix. T cells were analyzed using 11-color polychromatic flow cytometry. CD4 and CD8 T cells were characterized as 1] Naive (N), 2] Central Memory (CM) and 3] Effector Memory (EM) based on the expression of CD45RO and CD27. Terminal Effector (TE) cells and Effector (E) cells were identified based on CD45RO and CD57 expression. The activation state of each T cell sub-population was analyzed by measuring 1] CD107, 2] IFN- γ , 3] IL-2 and 4] TNF- α production. Polyfunctional responses were defined as indicated in the figure.

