13.4 Polyfunctional Analysis

Using our tiered approach to immune monitoring, if a CMV pp65 specific immune response is detectable by ELISpot assay, a polyfunctional analysis of 10-12 markers of T-cell phenotype and function will be performed. PBMCs will be stained for the surface markers CD3 (to identify it as a T cell), CD4 (to define as specific helper cell), CD8 (to define antigen specific cytotoxic T cells). The maturation state and the activation status of samples will be detected by polychromatic flow cytometry using optimized panels which will include CCR7, CD45RA, HLA-DR, and CD69. Levels of naïve (TN – CD45RA+CCR7+), central memory (TCM – CD45RA-CCR7+), effector memory (TEM – CD45RA-CCR7-), or terminally differentiated effector memory (TEMRA – CD45RA+CCR7+). To determine T-cell reactivity to *the vaccine* we will include antibodies specific against the intracellular cytokines IFN- γ , TNF- α , IL-2 and CCL3, CD107a along with a vital-dye reagent. Briefly, cryopreserved PBMC samples will be thawed and rested overnight at 37°C/5% CO₂ in RPMI media containing 10% fetal calf serum. Cells are adjusted to 2x10⁶/well with or without stimulation with a mixture of the peptides to Component A in the vaccine in the presence of Brefeldin A (5 μ g/ml Sigma-Aldrich, St. Louis, MO) monensin (1 μ g/ml; Golgistop, BD Biosciences, San Diego, CA), and antibodies against CCL3 and CD107a for 5-6 hr at 37°C and 5% CO₂. Following stimulation, cells will be treated with EDTA for 15 minutes at ambient temperature (AT, 18-22°C). The cells will be washed, and stained with MAbs specific for CD4, CD8, CCR7, CD45RA, and HLA-DR, and a vital-dye reagent (LIVE/DEAD) for 20 minutes at AT. After two washes, 1x BD FACS Lysing solution (BD Biosciences, San Jose, CA) will be added and samples will be incubated for 10 minutes at AT. After one wash, 1x BD FACS Permeabilizing Solution 2 (BD Biosciences, San Jose, CA) will be added and samples incubated for 10 minutes at AT. After one wash, cells will

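### The polyfunctionality score in section 15.4.3 counts positive markers per patient, not functions per cell, so a mix of single-function T-cell subsets can score the same as cells carrying all five functions

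*Combined protocol and SAP*

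**What the plan says.** The question is set in section 8.1 as an exploratory hypothesis: "The quality of immune responses determined by polyfunctional flow cytometry is multifunctional or monofunctional using the pp65 peptide in PEP-CMV". Section 9.4 gives the biological meaning and attaches it to the cell: "chronic infections often are typified by reactive T cells that are mono- or dual-functional".

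The score is built in section 15.4.3 in three steps.

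- Positivity: "For each measure, a lower threshold corresponding to two standard deviations above background is set to 0 based on a Poisson model", which the plan describes as "essentially allowing T-cells to be designated as positive or negative for a certain phenotypic marker".
- Score: "The number of positive phenotypic markers post-vaccination will be calculated for each patient".
- Arm comparison: "The Kruskal-Wallis test will be used to compare treatment arms with respect to the number of phenotypic markers observed post-vaccination 3", and again at vaccination 6. Fisher's exact test then compares the "proportion of patients with 5 positive markers, and 4 or more positive markers".

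Section 13.4 decides who is assayed: "if a CMV pp65 specific immune response is detectable by ELISpot assay, a polyfunctional analysis of 10-12 markers of T-cell phenotype and function will be" carried out. Section 13.2 adds that the assay also depends on enough cells being available. Section 15.4.3 frames its analyses on patients evaluable for the primary immunologic endpoint and does not say how unassayed patients are handled.

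**The concern.** No written step combines markers within a cell. Each marker is judged alone, and the positives are added up for the patient. That total says how many functions appear somewhere among the patient's T cells. It does not say whether any one cell performs several of them, which is how sections 8.1 and 9.4 pose the question.

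At stake is the reading of one exploratory objective. If the arms differed in co-expression but not in which markers are detectable, the planned tests could show no difference. If both arms scored high, the report could call the response polyfunctional without evidence of multifunctional cells.

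A second, smaller matter is the population. The assay is run after a detectable ELISPOT response, and ELISPOT is the primary randomised comparison. The arm comparison of quality is therefore conditional on a post-randomisation result, and the plan does not label it so.

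**Working it through.** The plan gives no power or error rate for this endpoint, so there is no figure to reproduce. The check takes the score as written and asks what it returns for two opposite kinds of response.

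**Inputs from the documents.** At least 500,000 lymphocytes per sample and an expected responding frequency of 0.05% to 1.0% (section 13.4); five functions stained: IFN-gamma, TNF-alpha, IL-2, CCL3 and CD107a (section 13.4); threshold of 2 SD above background under a Poisson model (section 15.4.3); 13 evaluable patients per arm (section 15.1).

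**Assumptions.** Background per marker is not given; the range 0.01% to 0.1% is used. Frequencies are applied to all 500,000 events. A score of 5 is taken as the maximum, inferred from the five functions and the cut-points.

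**Step 1: identical marginal frequencies.** Patient X has one 0.1% subset carrying all five functions. Patient Y has five separate 0.1% subsets with one function each, 5 × 0.1% = 0.5% in total, inside the plan's range. For every marker, both have 500,000 × 0.001 = 500 positive cells. At the highest assumed background (0.1%, 500 cells) the threshold is 2 × √500 = 44.7. The net count has mean 500 and SD √(500 + 500 + 500) = 38.7, so each marker clears the threshold by (500 − 44.7)/38.7 = 11.8 SD. Both patients score 5, though no responding cell in Y has more than one function.

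**Step 2: where the score stops saturating.** A response *f* split equally over five single-function subsets gives 500,000 × *f*/5 cells per marker. Simulated probability that this patient scores 5:

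| Total response | Background 0.01% | 0.05% | 0.1% |
|---|---|---|---|
| 0.05% | 0.99 | 0.30 | 0.06 |
| 0.1% | 1.00 | 0.99 | 0.79 |
| 0.25%, 0.5%, 1.0% | 1.00 | 1.00 | 1.00 |

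A patient whose responding cells all carry five functions scored 5 with probability 1.00 in every cell of the table.

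Hand check of one entry (0.05% response, 0.05% background): 50 signal cells per marker, 250 background cells, threshold 2 × √250 = 31.6, SD √(50 + 250 + 250) = 23.5. The chance that one marker is positive is Φ((50 − 31.6)/23.5) = Φ(0.78) = 0.78, and 0.78 to the fifth power is about 0.29, in line with the simulated 0.30.

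**Step 3: arm comparison, extreme contrast.** One arm has only single-function subsets; in the other, every responding cell carries five functions; 13 patients each. Over 2,000 simulated trials in each of three settings (response 0.25% with background 0.01%; 0.5% and 1.0% with background 0.05%), the planned Kruskal-Wallis test and the Fisher test on 5 markers rejected at 0.05 in 0% of trials. If all 26 patients score 5, Fisher gives 13/13 against 13/13, p = 1.0, and the rank test has only ties. An ideal per-cell measure would give 0/13 against 13/13, with two-sided p = 2/C(26,13) = 2/10,400,600 = 1.9 × 10⁻⁷.

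**The case against.** The strongest defence is that section 15.4.3 adopts a method by reference. It cites two publications, and the Figure 5 legend in section 9.4 says that polyfunctional responses are defined in that figure, which is not reproduced in the text available. The positivity rule also speaks of T-cells being designated, so the patient count may summarise a cell-level classification. This stands as a limit on the conclusion: the laboratory may already gate combinations. It does not repair the written score, which goes from single-marker positivity to a patient total. The Figure 5 legend lists four functions, so it cannot by itself define a five-marker score.

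Three stronger readings are tempting and are not supported.

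- A reader might infer that the score cannot tell a multifunctional from a monofunctional response at all. It can in part. Section 9.4 describes chronic responses as largely restricted to IFN-gamma and TNF-alpha; such a response scores 2, and a single-cytokine response scores 1. The failure arises when different cells make different single products that together cover the panel, and nothing in the documents says that this pattern is expected.
- A reader might infer that lineage and maturation markers inflate the count, because section 15.4.3 refers to phenotypic markers and the panel has 10-12. The documents do not show this. Data are background-subtracted, a cells-alone control is run, and the cut-points of 5 and 4 or more match the five functions. The set still needs naming.
- A reader might infer that ELISPOT-negative patients leave the Fisher denominator. The plan does not say so; it is silent. Assessing quality among responders is a legitimate question, and scoring negatives as zero answers a different one.

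It is also fair that the endpoint is exploratory, that section 15.4.3 allows additional analyses, and that Step 3 is an extreme contrast.

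**Conclusion.** The point holds in this form: as written, the score measures breadth of markers per patient rather than co-expression per cell. A response made of different single-function subsets can score 5, the same as one whose cells carry all five functions. Whether it does depends on signal and background. Under the assumed backgrounds it is near-certain from 0.25% total response upward, but the probability falls to 0.30 and 0.06 at 0.05% response with backgrounds of 0.05% and 0.1%. So the claim is that it can score 5, not that it will.

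The conclusion rests on the plain wording of section 15.4.3 and on 5 being the top score; the cited references could not be consulted. The consequence is confined to one exploratory objective. The primary ELISPOT comparison and its stated 81% power are untouched. The change is worth making because the data needed for the better measure will already exist. The conditioning on ELISPOT response is a matter of labelling and sensitivity analysis, not a demonstrated bias.

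**What to change.** Amend section 15.4.3 before analysis.

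1. Name the five functions: IFN-gamma, TNF-alpha, IL-2, CCL3 and CD107a.
2. Derive the endpoint by Boolean gating of these functions on the same acquired events, within CD4 and CD8 separately.
3. For each patient, report the background-subtracted percentage of T cells co-expressing at least 4 functions, and all 5. Compare arms on it with the planned rank test.
4. For the Fisher tests, call a patient polyfunctional only if that co-expressing subset exceeds the 2-SD background threshold.
5. Label the comparison as among ELISPOT responders. Add a sensitivity analysis over all evaluable patients that counts ELISPOT-negative patients as not polyfunctional and treats those unassayed for lack of cells as missing. State the first rule as an assumption: a negative IFN-gamma ELISPOT does not exclude the other four functions, so it matters for the 4-or-more category.

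The cost is plan wording and gating of data already collected; the functions are stained and acquired together, so no new sample or assay is needed. The downside is that small Boolean subsets are noisier and reported proportions will be lower. If the laboratory already gates combinations, items 1 to 4 only put that practice in writing.
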